### 1.2 Secondary Objectives:

(a) To test the effects of telephone-based ACT on sleep interference, engagement in daily activities, and quality of life (QoL) in MBC patients.

*H2:* ACT will lead to improved secondary outcomes of sleep interference, engagement in daily activities, and QoL as compared to education/support.

(b) To examine change in psychological flexibility as a mediator of ACT's effect on fatigue interference.

*H3:* Increases in psychological flexibility will mediate the beneficial effect of ACT on fatigue interference.

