### 2.2 Secondary Outcome Measures:

(1) Sleep interference will be assessed with the 8-item PROMIS sleep-related impairment measure. This measure assesses the perceived interference of sleep problems with activities, mood, and cognition.

(2) Engagement in daily activities will be assessed with the 6-item PROMIS short-form measure of ability to participate in social roles and activities. The items,

which are reverse-coded, measure difficulty engaging in social and recreational activities as well as usual work (including housework).

(3) QoL will be measured with the 27-item FACT-G, consisting of four subscales: Physical Well-Being, Social/Family Well-Being, Emotional Well-Being, and Functional Well-Being. An overall score is computed to represent general QoL.

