Primary objective (2.1): To test the effect of telephone-based ACT on fatigue interference in MBC patients. A linear mixed-model repeated measures approach (SAS Proc-Mixed) will be used to test the hypothesis (#1) that ACT will improve fatigue interference as compared to the education/support condition. The model will include the main effect of time (as categorical) and study group (ACT vs. education/support) and the time-by-study group interaction. A treatment effect will be evidenced by a significant interaction between time and study group. If the treatment effect is significant, follow-up tests will be conducted to examine group differences at each follow-up, controlling for the outcome at baseline.

Statistical power. Our sample size is calculated based on the estimated difference between study conditions (ACT vs. education/support) on the primary outcome of fatigue interference at 2 weeks post-intervention. In our pilot study, we found a moderate effect ( $d = -.30$ ) of study condition on fatigue interference at 1 month post-intervention. It should be noted that only about half of the pilot sample had elevated fatigue interference at baseline (unlike the proposed study, the pilot study did not require all eligible patients to have clinically significant levels of fatigue interference); thus, the effect size is likely to be higher in the proposed study where the sample will have uniformly elevated fatigue interference at study entry. Indeed,

among patients with moderate to severe baseline fatigue interference in our pilot study, we found a strong effect ( $d = -.59$ ) of study condition on fatigue interference at 1 month post-intervention. Thus, we conservatively estimate a medium effect size of  $d = -.40$  at 2 weeks post-intervention. With a sample size of 198 patients at 2 weeks post-intervention (assuming 21% attrition), we will have 80% power ( $p = .05$ , two-tailed) to detect a Cohen's  $d$  of  $-.40$  in a linear mixed model. At the final, 6-month follow-up with a sample size of 163 (assuming 35% attrition), we will have 80% power ( $p = .05$ , two-tailed) to detect a Cohen's  $d$  of  $-.44$ .

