Secondary objective (2.2a): To test the effects of telephone-based ACT on secondary outcomes in MBC patients. Linear mixed models will be run in SAS Proc-Mixed to test the hypothesis (#2) that ACT will improve sleep interference, engagement in daily activities, and QoL as compared to the education/support condition. Each model will include the main effect of time (as categorical) and study group and the time-by-study group interaction. A treatment effect will be evidenced by a significant interaction between time and study group. Probabilities for secondary outcomes will be Sidak adjusted for correlated multiple outcomes to control the familywise Type I error rate. If treatment effects are significant, follow-up tests will be conducted to examine group differences at each follow-up, controlling for the outcome at baseline.

Secondary objective (2.2b): To examine change in psychological flexibility as a mediator of ACT's effect on fatigue interference. The PROCESS macro for SAS developed by Andrew Hayes will be used to test the hypothesis (#3) that increases in psychological flexibility will mediate the effect of ACT on fatigue interference. This analysis employs ordinary least squares regression. Bootstrapped confidence intervals will be computed for the indirect effect of study group on fatigue interference at 2 weeks post-intervention (via change in psychological flexibility over the same time period). The analysis will control for baseline levels of the mediator and outcome. We will also compute the indirect effects of study group on fatigue interference at 3 and 6 months post-intervention (via change in psychological flexibility at 2 weeks post-intervention). These analyses will also control for baseline levels of the mediator and outcome.

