Exploratory objective (2.3): To explore changes in the two core aspects of psychological flexibility (i.e., mindfulness/acceptance and commitment/behavior change) as mediators of ACT's effect on fatigue interference. The PROCESS macro for SAS will be used to explore the extent to which changes in mindfulness/acceptance and commitment/behavior change processes mediate the effect of ACT on fatigue interference. Both potential mediators will be entered into the same model. Bootstrapped confidence intervals will be computed for the indirect effect of study group on fatigue interference at 2 weeks post-intervention (via change in mindfulness/acceptance and commitment/behavior change processes over the same time period). The analysis will control for baseline levels of the mediators and outcome. We will also compute the indirect effects of study group on fatigue interference at 3 and 6 months post-intervention (via changes in mindfulness/acceptance and commitment/behavior change processes at 2 weeks post-intervention). These analyses will also control for baseline levels of the mediators and outcome.

Other exploratory analyses. To inform future research, we will explore the extent to which sociodemographics (e.g., age, education) and clinical characteristics (e.g., cancer treatments, baseline fatigue severity) moderate the effects of ACT on primary and secondary outcomes. For

these analyses, we will use linear mixed modeling at a two-sided significance level of 0.05. Preliminary findings or hypotheses generated from these moderation analyses will be further tested in a future trial.

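### The Sidak adjustment of the three secondary outcomes names no formula, familywise level or step-down rule; if ordinary single-step Sidak is meant, Holm-Sidak is a free improvement

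*Combined protocol and SAP*

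**What the plan says.** Section 1.2 states H2: "ACT will lead to improved secondary outcomes of sleep interference, engagement in daily activities, and QoL as compared to education/support". Section 2.2 makes quality of life a single endpoint, since for the FACT-G "An overall score is computed to represent general QoL". The family therefore has three members.

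In Section 7.0, under secondary objective (2.2a), each outcome has its own mixed model with categorical time, and "A treatment effect will be evidenced by a significant interaction between time and study group". With four assessment times and two arms, that is one 3-df test per outcome. On multiplicity the section says only: "Probabilities for secondary outcomes will be Sidak adjusted for correlated multiple outcomes to control the familywise Type I error rate".

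No Sidak formula, familywise level, correlation value or single-step/step-down wording is given anywhere. The .05 level appears for the primary power calculation and for the exploratory moderation analyses ("we will use linear mixed modeling at a two-sided significance level of 0.05"), but not for this family.

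**The concern.** The sentence can be read in more than one way, and the readings differ in what they deliver.

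- **Ordinary single-step Sidak.** Every outcome is held to the strictest level even after another has been rejected. A step-down version has the same familywise guarantee and is never stricter, so single-step gives up power for nothing. The loss is largest when all three effects are real, which is what H2 predicts.
- **An adjustment that uses the correlation.** The words about correlated outcomes suggest this. Some such rules hold 5%. A commonly programmed weighted form does not.

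At stake is the number of secondary claims the trial can support, and whether the error control the plan promises is delivered.

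**Working it through.** **Inputs from the documents.** Three outcomes; N = 198 at 2 weeks after 21% attrition from 250; d = .40; two-tailed .05; 80% power. All of the power figures are for the primary outcome.

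**Assumed.** Familywise level .05; 1:1 allocation; 80% stand-alone power for each secondary outcome; equal correlation r between the three test statistics, taken as .5 with .3 and .7 as a range. The plan gives no effect sizes or correlations for the secondary outcomes.

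**1. The plan's own figure.** A two-sample t-test with 99 per arm, d = .40 and two-sided .05 has power .800. This reproduces "With a sample size of 198 patients at 2 weeks post-intervention (assuming 21% attrition), we will have 80% power".

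**2. Levels.** Single-step Sidak: 1 − .95^(1/3) = .01695 for each outcome. Holm-Sidak, smallest p first, stopping at the first non-rejection: 1 − .95^(1/3) = .01695, then 1 − .95^(1/2) = .02532, then .05. Without adjustment, three independent tests would have familywise error 1 − .95^3 = .143.

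**3. Dominance.** No Holm-Sidak level is below .01695, so any p-value rejected by single-step Sidak is also rejected by Holm-Sidak. This is arithmetic and needs no assumption about effects or correlation. Example: p = .010, .020, .040 gives one rejection under single-step Sidak and three under Holm-Sidak.

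**4. Familywise error with no real effect (simulated).** The two procedures are identical: .048, .045 and .040 at r = .3, .5 and .7. The 3-df tests give .049, .046 and .041.

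**5. Power at r = .5.** Trivariate normal simulation, with the mean shifted by 1.960 + 0.842 = 2.802 for each real effect:

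| Real effects | Quantity | Single-step Sidak | Holm-Sidak |
|---|---|---|---|
| 3 | average power | 66% | 74% |
| 3 | all three claimed | 42% | 59% |
| 3 | at least one claimed | 87.5% | 87.5% |
| 2 | both claimed | 51% | 57% |
| 1 | claimed | 66.0% | 66.1% |

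For all three claimed, r = .3 gives 37% against 55% and r = .7 gives 48% against 64%. With 3-df tests at r = .5 the result is again 42% against 59%.

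The plan's two pilot effects at N = 198 give a range for three real effects. At d = .30, average power is 39% against 45%, and all three are claimed in 16% against 29%. At d = .59, the figures are 96% against 98% and 91% against 96%. These d values are single-visit contrasts on the primary outcome, so they only set a scale for a 3-df interaction test.

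**6. False rejection of a null outcome when others are real, r = .5.** With one real effect, 3.2% rises to 4.1%. With two, 1.7% rises to 3.6%. The highest value over r = .1 to .9 is 4.4%.

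**7. The correlation-weighted reading.** The level is 1 − .95^(1/3^(1−r)), which is .0235, .0292 and .0362 at r = .3, .5 and .7. Simulated familywise error with no real effect is about 6.6% to 6.7%, 7.6% and 8.1% (3-df tests: 6.8%, 7.7% and 8.4%).

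**The case against.** **Single-step Sidak is valid.** It does what the plan asks. A Phase II trial need not use the most powerful procedure for its secondary outcomes, and nothing here touches the primary analysis. All of that stands; the point is an improvement and does not correct an error.

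**The plan mentions correlation, so ordinary Sidak may be the wrong comparator.** This also stands, and it limits the claim.

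- Holm-Sidak does not dominate every rule the sentence could mean. Against a single-step Sidak calibrated exactly to the correlation, it is weaker when only one effect is real: 66.1% against 67.4% at r = .5, and 66.0% against 73.1% at r = .9. It is stronger for claiming all three: 59% against 44% at r = .5, and 68% against 64% at r = .9.
- Against the weighted form, p = .020, .028, .20 at r = .5 gives two rejections to Holm-Sidak's none. That form gets there by exceeding 5%.

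**A reader might infer that the plan inflates Type I error.** That follows only if the weighted form is intended, and the documents do not say so.

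**A reader might also infer that the secondary outcomes need more patients.** At d = .40 and N = 198, the level .0170 does lower single-test power from 80% to 66%. That is the price of the first-step level, which Holm-Sidak keeps, so it does not measure the missing step-down rule. The plan also makes no power claim for secondary outcomes.

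**The power figures rest on assumptions.** They do. The thresholds at familywise .05 and the dominance over ordinary Sidak do not depend on them.

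**Conclusion.** The point holds in a conditional form and is minor. The multiplicity sentence leaves the formula, the familywise level and the stepping rule open.

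- If ordinary single-step Sidak is meant, it is valid but dominated by Holm-Sidak. The gain falls on the second and third claims: 8 points of average power and 17 points for claiming all three, with three real effects, 80% stand-alone power and r = .5. It is 6 points for claiming both of two real effects, and about nothing when one is real. The chance of at least one claim does not change.
- If the weighted form is meant, familywise error would exceed the assumed 5% at each correlation tried, against the plan's stated aim.

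The documents do not settle which reading applies. They support neither a finding of inflated error nor one of inadequate sample size.

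**What to change.** In Section 7.0, secondary objective (2.2a), replace the Sidak sentence with one such as: *The three time-by-group interaction p-values will be tested by the step-down Holm-Sidak procedure at two-sided familywise .05 (levels .0170, .0253 and .05, smallest p first, stopping at the first non-rejection).* If the correlation between outcomes is meant to enter, name instead a step-down method that holds 5% under that correlation. In simulation, the step-down form of the correlation-exact Sidak matched or beat Holm-Sidak (all three claimed at r = .9: 71% against 68%). The change should be made before outcome data are seen by arm.

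The cost is one sentence, with no added patients or data, and no ordinary-Sidak rejection is lost. There are three downsides:

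- False rejection of a null outcome alongside real ones rises, but stays below 5% (step 6 of the working).
- Simple simultaneous confidence intervals matching the test are no longer available. The plan specifies none for these outcomes; its only stated intervals are the bootstrapped ones for mediation.
- Holm-Sidak is weaker than a correlation-exact single-step Sidak when only one effect is real: slightly at r = .5, more at very high correlation.

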## 7.0 Statistical Considerations

Design and data considerations. The primary and secondary outcomes in the proposed study are scaled continuously. For these outcomes, a linear mixed model using the SAS procedure MIXED will be employed. Because parameter estimation in MIXED employs full information maximum likelihood, all data the individual provides are included in the analysis even if some of the data are missing.

Preliminary analyses: Distributional issues. Univariate and descriptive analyses will be performed on all dependent variables, and if necessary, normalizing and/or variance stabilizing transformations will be sought in the family of power transformations and applied to the data before inferential analyses are undertaken. Missing data/subject attrition. We anticipate some missing data due to participant death, medical factors, and other reasons. For individuals who complete the first assessment but withdraw from the study, we will examine demographic, medical, and symptom factors that might be predictive of dropout using logistic regression. In the analyses for the primary and secondary objectives described below, all randomized participants will be included in intent-to-treat analyses, as the aims are concerned with the impact of the intervention on outcomes regardless of study completion status. Second, for participants who miss assessments, it is possible that attrition may be related to the study condition to which they have been assigned. We plan to use the random effects pattern-mixture model proposed by Hedeker and Gibbons to address missing data. Analyses of potential covariates. Because patients will be randomly assigned to the two study conditions, significant differences on the baseline values of all measured variables are not expected. T-tests and chi-square analyses will be performed to determine whether there are differences between the groups on potential baseline covariates (e.g., demographic and medical variables), and if there are differences these variables will be used as covariates in subsequent analyses.

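### The H3 mediation models have no missing-data method that fits them: run as written they use complete rows only, and the 3- and 6-month indirect effects could be improved cheaply

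*Combined protocol and SAP*

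**What the plan says.** Section 1.2 lists H3 as secondary objective (b): "To examine change in psychological flexibility as a mediator of" the ACT effect on fatigue interference. Section 7.0 takes it up as secondary objective (2.2b).

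On the analysis population, Section 7.0 states: "In the analyses for the primary and secondary objectives described below, all randomized participants will be included in intent-to-treat analyses". The reason given is "as the aims are concerned with the impact of the intervention on outcomes regardless of study completion status".

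On missing data, the same section makes four statements:
- For the mixed models: "Because parameter estimation in MIXED employs full information maximum likelihood, all data the individual provides are included in the analysis".
- As a general plan: "We plan to use the random effects pattern-mixture model", to deal with missing data.
- On the cause of loss, it expects death and medical factors among others, and grants that "it is possible that attrition may be related to the study condition to which they have been assigned".
- For patients who withdraw: "we will examine demographic, medical, and symptom factors that might be predictive of dropout using logistic regression".

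For H3 it turns to the PROCESS macro: "This analysis employs ordinary least squares regression". Indirect effects on fatigue interference are estimated separately at 2 weeks, 3 months and 6 months, always through the change in flexibility to 2 weeks. Baseline mediator and outcome are adjusted for, and intervals are bootstrapped. No imputation, weighting or analysis set is named for these regressions.

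**The concern.** Full-information likelihood in PROC MIXED works because one model holds all of a patient's repeated scores. A random-effects pattern-mixture model likewise needs repeated scores and random effects. A least-squares regression of one outcome at one visit has neither. Bootstrapping gives an interval for the rows used; it does not bring back rows with a missing score.

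Without an added step, a patient therefore needs both the 2-week mediator and the later outcome to count. This matters most for the 3- and 6-month effects. The arm-to-mediator path concerns 2 weeks only, yet in the 6-month model it is estimated without patients whose 2-week mediator is on file but who left later. Their 3-month scores go unused too.

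Complete-row regression is valid when dropout depends only on arm and the baseline mediator and outcome, given correctly specified linear models. The plan's own expectations about attrition do not allow that to be taken for granted. At stake is the size of the later indirect effects, and so how firmly H3 can be claimed.

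**Working it through.** **The plan's own figures** (Section 7.0, Statistical power; N = 250 with 21% and 35% attrition):
- 2 weeks: 250 × 0.79 = 197.5, stated as 198.
- 6 months: 250 × 0.65 = 162.5, stated as 163.
- Power, two-sided 0.05, equal arms assumed: Φ(d√(N/4) − 1.96). For d = 0.40 and N = 198 this is Φ(0.854) = 80.4%. For d = 0.44 and N = 163 it is Φ(0.849) = 80.2%. The noncentral t gives 80.0% and 79.7%.

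The figures reproduce. They concern the primary outcome; no power is stated for an indirect effect.

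**Rows available to H3**
- 2-week model: at most 198/250 = 79%, so at least 52 are left out.
- 6-month model: at most 163/250 = 65%, so at least 87 are left out.
- Assessed at 2 weeks but not at 6 months: at least 198 − 163 = 35, or 14% of 250. This bound does not need dropout to be monotone.
- 3-month model: no attrition is stated.

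**Illustrative simulation.** All coefficients are assumptions. n = 250, allocation 1:1, monotone loss of 21%, 28% and 35% (the 28% is assumed). A is arm, M flexibility and Y fatigue, in SD units, with corr(M0, Y0) = −0.4:
- M2 = 0.4A + 0.6M0 + e(SD 0.8)
- Y2 = −0.3M2 − 0.15A + 0.5Y0 + e(0.75)
- M3 = 0.5M2 + 0.2M0 − 0.1Y2 + e(0.7)
- Y3 = 0.55Y2 − 0.12M2 + 0.15Y0 + e(0.65)
- Y6 = 0.5Y3 + 0.2Y2 − 0.05M2 + 0.1Y0 + e(0.65)

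Effect of M2 on Y3: 0.55 × (−0.3) − 0.12 = −0.285. On Y6: 0.5 × (−0.285) + 0.2 × (−0.3) − 0.05 = −0.2525. True 6-month indirect effect: 0.4 × (−0.2525) = −0.101.

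Bias in the 6-month indirect effect (positive means mediation is overstated):

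| Dropout follows | Logit slope | Complete rows | In SE | Imputed by arm |
|---|---|---|---|---|
| Arm and baseline fatigue | 0.6 and 0.8 | +0.4% | 0.01 | about 1% or less |
| Preceding fatigue, both arms | 0.25 / 0.5 / 1.0 | −0.5 / −1.8 / −6.1% | 0.01 / 0.04 / 0.14 | about 1% or less |
| Preceding fatigue, ACT only | 0.5 / 1.0 / 1.5 | about +4 / +5.5 / +7% | 0.08 / 0.11 / 0.15 | about 1% or less |
| Low preceding flexibility, ACT only | 0.5 / 1.0 / 1.5 | about +10 / +20 / +27% | 0.21 / 0.39 / 0.52 | about 1% or less at 0.5 and 1.0; not run at 1.5 |

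The first three rows rest on 8,000 replicates (Monte Carlo error about 0.3 points), the last on 3,000 (about 0.5 to 0.7 points). Worked example, both arms, slope 1.0: full data −0.1010, complete rows −0.0948; 0.0062/0.1010 = 6.1%, and 0.0062/0.0450 = 0.14 SE.

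**Precision.** Standard errors, complete rows against imputed: 0.0450 and 0.0452 (fatigue, both arms, slope 1.0); 0.0486 and 0.0452 (fatigue, ACT only, 1.0); 0.0524 and 0.0459 (flexibility, ACT only, 1.0).

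**Where the bias enters.** A second, large-sample simulation with other assumed paths (a = 0.4, b = −0.4, product −0.16; 35% lost in one step) gave a = 0.626, b = −0.397 and a product of −0.248 when ACT dropout followed the 2-week mediator. ACT patients with low flexibility leave, so those who stay make the arm-to-mediator path look stronger.

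**Where imputation does not help.** At 2 weeks, with loss driven by the unseen 2-week fatigue score (2,000 replicates), the true −0.120 became −0.111 with complete rows and −0.111 with imputation (−7.6% against −7.4%). Under monotone loss, a patient missing at 2 weeks has only baseline data to impute from.

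**The case against.** The strongest reply is about weight. When dropout follows fatigue, the bias is at most 0.15 SE in these runs. By the normal approximation a 95% interval then covers Φ(1.81) − Φ(−2.11) = 94.7%, which hardly matters, and in the both-arms case imputation gains little or no precision. This stands for those scenarios. It is not a general ceiling: at 0.52 SE the same formula gives Φ(1.44) − Φ(−2.48), about 92%, and nothing in the documents rules that mechanism in or out.

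A second reply concerns reading. The reason given for including everyone speaks of the impact of the intervention on outcomes. That fits H1 and H2 better than a question of mechanism, and an indirect effect is not an intent-to-treat contrast. This is fair. A reader might infer that the plan contradicts itself, or prescribes listwise deletion for H3. The documents support neither: they do not mention deletion, do not rule out imputation, and word the pattern-mixture sentence generally. What stands is a gap. H3 falls within the words of the all-randomized sentence, and no named method can deliver that for these regressions.

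Third, the plan does attend to attrition, through the dropout regression and the general pattern-mixture sentence. Neither supplies an estimator for rows missing from a single-outcome regression.

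**Conclusion.** The point holds as a cheap improvement to a secondary analysis. Under the plan's own attrition, H3 as written rests on at most 79% of randomized patients at 2 weeks and at most 65% at 6 months. At least 35 patients with 2-week scores are left out of the 6-month model. These counts need only the stated attrition and no added missing-data step.

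The bias cannot be sized from the documents. Across the assumed mechanisms in the table it ran from about −6% to about +27% at 6 months, and it is close to nil if dropout depends only on arm and the baseline scores. No upper bound should be claimed. Nor should a reader infer that the H3 result will be biased, or that mediation will be overstated: the direction changes with the mechanism, and the coefficients are assumptions.

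H1, H2 and the sample size are unaffected, and no gain is shown for the 2-week indirect effect. The exploratory mediation models (Section 7.0, objective 2.3) have the same gap, although the all-randomized sentence does not name exploratory objectives.

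**What to change.** In Section 7.0, secondary objective (2.2b), for the 3- and 6-month indirect effects, specify one of:
- multiple imputation by arm, using mediator and outcome scores from all assessments, followed by the planned regressions, with a stated way of combining imputation and bootstrap intervals (for example, imputing within each bootstrap sample); or
- a full-information maximum-likelihood path model that includes the intermediate scores.

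Keep complete-case least squares as a sensitivity analysis, and state how scores after death are handled. The 2-week model can stay complete-case if its analysis set is defined. Merely limiting the all-randomized sentence to H1 and H2 and defining an H3 analysis set would make the text consistent, but would leave the later estimates as they are.

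The cost is a paragraph of SAP text and modest programming, with no new data. Both methods rely on data missing at random and do not repair loss driven by unseen scores. The gain ranges from nil to material, depending on the dropout mechanism.

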#### Interview Procedures

MBC patients ( $N = 250$ ) who are eligible and provide informed consent will complete assessments at baseline and approximately 2 weeks, 3 months, and 6 months following the final intervention session (see Table 1 in section 5.0 above for allowable assessment windows). The baseline assessment takes about 35 minutes, and each follow-up assessment takes about 30 minutes. Assessments will include questions regarding demographics, medical history, primary and secondary outcomes, and potential mediating variables. Participants will be provided with copies of response options via email or postal mail to facilitate survey completion (see Appendix E). Each participant will receive \$40 in Target gift cards via postal mail for each completed assessment (baseline and 2-week, 3-month, and 6-month follow-ups) for a possible total of \$160 in gift cards for their time. Participants will not receive gift cards for the 6, 50-minute intervention sessions. There is no cost to study participants. Table 2 below outlines the assessment schedule at baseline and the three follow-ups.

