**Table 2. Measures**

Domain	Measure	# Items	Baseline	2-week follow-up	3-month follow-up	6-month follow-up
Sociodemographics	Sociodemographics	7	X			
Medical comorbidity	Checklist of 9 conditions	9	X			
Functional status	Patient-reported ECOG	1	X	X	X	X
Cancer information (e.g., date of diagnosis, cancer treatments)	Chart review	n/a	X	X	X	X
Physical and mental healthcare use	Healthcare use interview	7 (6 at follow-up)	X	X	X	X
Medications	Medication interview	n/a	X	X	X	X
Primary outcome: fatigue interference	Fatigue interference subscale of FSI	7	X	X	X	X
Secondary outcomes:						
• Sleep interference	PROMIS short-form sleep-related impairment measure	8	X	X	X	X
• Engagement in daily activities	PROMIS short-form measure of ability to participate in social roles and activities	6	X	X	X	X
• QoL	FACT-G	27	X	X	X	X
Hypothesized mediator: psychological flexibility	Acceptance and Action Questionnaire-II	7	X	X	X	X
Exploratory mediators: mindfulness/acceptance and commitment/behavior change	Cognitive and Affective Mindfulness Scale-Revised; Value Progress subscale of Valuing Questionnaire	15	X	X	X	X
Severity of symptoms: Fatigue severity, sleep disturbance, anxiety, depressive symptoms, pain, and cognitive symptoms	Fatigue severity and frequency items from FSI; PROMIS short-form measures of sleep disturbance, anxiety, depression, pain, hot flashes, and cognitive function	48	X	X	X	X

ECOG = Eastern Cooperative Oncology Group; FACT-G = Functional Assessment of Cancer Therapy-General; FSI = Fatigue Symptom Inventory; PROMIS = Patient Reported Outcomes Measurement Information System; QoL = quality of life.

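### H3 mediation models: the 2-week indirect effect is a concurrent association, and the lagged models adjust only for baseline, so a significant result can arise without mediation

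*Combined protocol and SAP*

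**What the plan says.** Section 1.2 words H3 causally: "Increases in psychological flexibility will mediate the beneficial effect of ACT on fatigue interference". Section 7.0, Secondary objective (2.2b), tests it with the PROCESS macro and bootstrap confidence intervals. On estimation it says: "This analysis employs ordinary least squares regression". The first model takes the "indirect effect of study group on fatigue interference at 2 weeks post-intervention (via change in psychological flexibility over the same time period"). Two later models estimate the indirect effect on "fatigue interference at 3 and 6 months post-intervention (via change in psychological flexibility at 2 weeks post-intervention"). On covariates for these the plan says "These analyses will also control for baseline levels of the mediator and outcome", and 2-week fatigue interference is not listed. The Exploratory objective (2.3) repeats the structure with two mediators, "via change in mindfulness/acceptance and commitment/behavior change processes over the same time period".

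In Table 2, the row "Hypothesized mediator: psychological flexibility" schedules the AAQ-II at baseline, 2 weeks, 3 months and 6 months, with nothing between baseline and 2 weeks. The short in-session forms described under ACT Intervention Procedures cover fatigue, anxiety and depressive symptoms, not flexibility. Under Interview Procedures, mediators and outcomes are asked together: "Assessments will include questions regarding demographics, medical history, primary and secondary outcomes, and potential mediating variables".

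The covariate paragraph of Section 7.0 adds only baseline variables on which the arms differ. No section states an assumption about mediator-outcome confounding, plans a sensitivity analysis for it, or fits a model in the reverse direction.

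**The concern.** An indirect effect is the product of two paths: group to mediator (a) and mediator to outcome (b). Randomisation supports a causal reading of a only. At 2 weeks both scores are self-reports from the same call. Three things can make b non-zero without flexibility acting on fatigue interference: a shared cause at that call (mood, disease state, answering style), ACT acting on the two scales in parallel, and lower fatigue interference raising the flexibility score. Baseline adjustment does not remove influences that arise after baseline.

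The later models put the mediator before the outcome, which helps. But a 3- or 6-month score carries forward part of the 2-week score, and without that score in the model some of the same-interview association passes into the lagged indirect effect.

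H3 is a stated secondary hypothesis and the trial's claim about mechanism. As planned, a significant interval cannot tell mediation from these alternatives. The primary analysis is not affected.

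**Working it through.** **Inputs from the plan.** N = 198 at 2 weeks and 163 at 6 months; d = -0.40 at 2 weeks; two-sided 0.05 (Section 7.0, Statistical power). The plan gives no power or error rate for the mediation test, so only its primary-outcome figures can be reproduced. Assuming 1:1 allocation, power = Φ(d√(N/4) - 1.96):
- 2 weeks: 0.40 × √49.5 = 2.814, and Φ(0.854) = 80.4% (80.0% by noncentral t).
- 6 months: 0.44 × √40.75 = 2.809, and Φ(0.849) = 80.2% (79.7% by noncentral t).
- Retention: 250 × 0.79 = 197.5 and 250 × 0.65 = 162.5.

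The stated sample sizes hold and are used below.

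**Size of the bias.** Let the true b be 0, let ACT shift flexibility by a (SD units), and let the 2-week residuals of the two scores correlate at -r with equal variances. The fitted b then tends to -r, and the indirect effect to -a × r. With a = 0.4 and r = 0.3 this is -0.12, or 0.12/0.40 = 30% of the ACT effect on the outcome. If a fraction 0.5 of the 2-week outcome carries to 6 months, the planned 6-month indirect effect tends to -0.4 × 0.3 × 0.5 = -0.06. Adding 2-week fatigue interference makes it 0, provided the shared cause does not act again later.

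**Simulation with true b = 0.** Planned OLS models, percentile bootstrap 95% interval for a × b, 500 resamples, 600 trials per cell (error up to about ±4 points). Assumptions not in the documents: SD 1, baseline-to-2-week coefficient 0.6, baseline mediator-outcome correlation -0.4, 6-month coefficient 0.5 on the 2-week outcome. Each cell gives the percentage of trials with a significant indirect effect: 2-week model / 6-month model as planned / 6-month model with 2-week fatigue interference added.

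| ACT shift in flexibility | r = 0 | r = 0.2 | r = 0.3 | r = 0.5 |
|---|---|---|---|---|
| 0 | 0 / 0 / 0 | 4 / 2 / 0 | 5 / 2 / 0 | 6 / 5 / 0 |
| 0.2 SD | 2 / 2 / 1 | 32 / 6 / 2 | 39 / 13 / 1 | 45 / 30 / 2 |
| 0.3 SD | 3 / 3 / 3 | 61 / 14 / 2 | 72 / 28 / 4 | 74 / 60 / 3 |
| 0.4 SD | 6 / 6 / 5 | 77 / 19 / 4 | 95 / 39 / 4 | 94 / 79 / 7 |
| 0.5 SD | 6 / 5 / 5 | 79 / 26 / 4 | 98 / 48 / 5 | 99.5 / 89 / 6 |

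At r = 0.1 the 2-week rate is 20%, 24% and 28% for shifts of 0.3, 0.4 and 0.5 SD. Over the whole grid, including r = 0.1 and 0.4, the adjusted model stays at 0 to 8%.

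**3-month model.** With N = 180 (assumed, between 198 and 163), both scales shifted 0.4 SD, baseline correlation -0.5 and carry-over 0.6, the planned model gave 25%, 51% and 83% at r = 0.2, 0.3 and 0.5. Repeat runs gave 27%, 44% and 82%, and a range of 32 to 91%. With 2-week fatigue interference added the first run gave 4%, 5% and 3%.

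**Reverse causation only.** ACT lowers fatigue interference by 0.40 SD, which then raises flexibility with path strength 0.2 to 0.5. Rates were 10 to 39% at 2 weeks and 3 to 31% at 6 months.

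**What the added covariate costs.**
- True mediation complete by 2 weeks (N = 180, b = -0.3 / -0.5): detection 91% / 93% in the 2-week model, 48% / 85% in the planned 3-month model, 6% / 6% in the adjusted 3-month model.
- True further effect of 2-week flexibility on the 3-month outcome (-0.2 / -0.3): power falls from 89% / 91% to 70% / 86%.
- No true effect, but a shared cause that persists (coefficient 0.3, shift 0.4 SD, r = 0.3 / 0.5): false positives at 6 months fall only from 85% / 87% to 47% / 51%. Other forms of persistence left 29 to 48%, and in one case 60 to 93%, after adjustment.

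**The case against.** The plan is better than a purely concurrent analysis. It computes indirect effects at three times, two with the mediator measured first, and it does not say that the 2-week model alone decides H3. Baseline adjustment removes confounding carried by the baseline scores. The two-mediator analysis is labelled exploratory. Unmeasured mediator-outcome confounding affects mediation analysis generally. All of this stands, and the lagged models are clearly the weaker offenders.

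A reader might infer that a false mediation finding is likely or nearly certain. The documents do not support that. They give neither the ACT effect on the AAQ-II nor the residual correlation, and the rates run from near 0 to almost 100% over the range tried. ACT is designed to raise flexibility, and the outcome includes mood, enjoyment and relations with others, so both conditions are plausible. Neither is quantified.

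A reader might also infer that the lagged model adjusted for 2-week fatigue interference should decide H3. That does not follow. The plan describes ACT as working on fatigue interference through flexibility and bases its sample size on the effect at 2 weeks, so much of any mediated effect may already be present then. The adjusted model removes exactly that part.

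**Conclusion.** The point holds in conditional form. H3 is tested with mediator change and outcome from the same 2-week interview, the lagged models omit 2-week fatigue interference, and nothing elsewhere in the plan offsets this.

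With no effect of flexibility on fatigue interference, the 2-week test is significant in more than half of simulated trials if ACT shifts flexibility by about 0.3 SD or more and the residual correlation is about 0.2 or more. The planned 6-month model passes one half only at a residual correlation of about 0.4 to 0.5 for shifts of 0.3 to 0.4 SD, or somewhat above 0.3 for a shift of 0.5 SD. If ACT does not move flexibility, the rates are about 5% or less. These figures rest on assumed correlations and carry-over, so they show what can happen and are not an estimate for this trial.

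Adding the 2-week outcome is informative but is neither a complete cure nor a neutral change. It asks a narrower question and fails against a confounder that persists.

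**What to change.** In Section 7.0, Secondary objective (2.2b), and likewise in the Exploratory objective (2.3):

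1. Label the 2-week indirect effect a concurrent association that cannot by itself support H3.
2. Keep the planned 3- and 6-month models, and report beside each the same model with 2-week fatigue interference as an added covariate. State that the added version estimates only the effect passed on after 2 weeks, and that it does not decide H3 alone.
3. State the assumption of no unmeasured mediator-outcome confounding, and add a sensitivity analysis for it. One form gives the indirect effect over a range of assumed residual correlations, with the value at which the interval first includes zero.

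This should be fixed before outcome data are examined, since a choice among these models made afterwards would carry little weight. No new data are needed: both measures are already taken at all four assessments. The cost is some SAP wording, a few more model runs and a more cautious claim about mechanism.
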